#### **4.6.5 Procedures for New MRI Findings**

In addition to any local reading according to local procedures and requirements, all MRI scans will be reviewed by an expert central reader within approximately 1 week of receipt and a report provided to the site. For the purposes of overall study relevant decisions and recommendations, including participant eligibility as well as for analysis, results from the expert central reader will be used. Any time the central reader identifies a new MRI finding the study center medical staff and the Sponsor will be rapidly notified (see Section [4.5.9](#)).

Refer to Section [5.1.2](#) for instructions in the event of new MRI findings (ARIA-E and ARIA-H).

#### **4.6.6 Assessments at Study Completion or Early Termination Visit**

Participants who complete the double-blind treatment period at Week 114 in scenario 1 or at Week 126 in scenario 2 (if applicable) will have to complete the final efficacy and safety assessment period 2 weeks following the last dose. Some participants may have already received the last study drug administration at Week 102 and performed the final efficacy and safety visit at Week 104 at the time of implementation of *the study extension by 12 weeks*.

All participants will be asked to come back for the follow-up assessments 14 weeks and 50 weeks after the last dose, unless they are transitioning to an OLE.

All participants who withdraw from treatment or discontinue from the study early (during the double-blind treatment period or during the OLE) will be asked to return 2 weeks after the last dose of study drug in order to complete the early termination visit.

In addition, participants who withdraw from treatment will be asked to return for collection of safety (except MRI) and limited efficacy data (i.e., the primary and secondary endpoints) at visits that have efficacy assessments per the schedule of activities until the end of the double-blind treatment period or until the last OLE follow-up visit (OLE Follow up 2) for those who enrolled in the OLE period.

Autopsy reports, including cause of death, for all participants who die during the study (i.e., prior to the Week 50 follow-up visit) should be requested.

Refer to the schedule of activities to be performed at the study completion in [Appendix 1](#).

#### **4.6.7 Follow-Up Assessments**

Participants who complete the double-blind treatment period and who are not willing to enroll in an OLE or these who complete the OLE period (defined as administration of at least three 510-mg doses Q4W) and are not willing to enroll in the WN42171 open-label study will be asked to return to the clinic 14 weeks and 50 weeks after the last dose of study drug for the follow-up visits (Follow Up 1 and Follow Up 2 or OLE Follow Up 1 and OLE Follow Up 2, respectively).

When participants complete the treatment period or discontinue early, every effort should be made to ensure that the safety follow-up period and all related assessments are completed.

After the study completion or early termination visit, adverse events should be followed as outlined in Sections [5.5](#) and [5.7](#). Refer to the schedule of activities (see [Appendix 1](#)) for the list of assessments to be performed at the follow-up visits.

#### **4.6.8 Unscheduled Assessments**

Assessments at unscheduled visits should be determined by the investigator based on clinical relevance and appropriateness to the cause of the unscheduled visit. The schedule of activities in [Appendix 1](#) allows for all assessments to be performed at unscheduled visits.

### **4.7 TREATMENT, PARTICIPANT, STUDY, AND SITE DISCONTINUATION**

#### **4.7.1 Study Treatment Discontinuation**

Participants must discontinue study treatment if they experience any of the following:

- Any medical condition that the investigator or Sponsor determines may jeopardize the participant's safety if he or she continues to receive study treatment
- Investigator or Sponsor determines it is in the best interest of the participant
- Pregnancy
- Upon evidence of more than 15 ARIA-H, cumulatively
- Any disseminated leptomeningeal hemosiderosis

All participants who withdraw from treatment will be asked to return 2 weeks after last dose in order to complete the early termination visit assessments.

In addition, participants who withdraw from treatment will be asked to return for collection of safety (except MRI) and limited efficacy data (i.e., the primary and secondary endpoints) at visits that have efficacy assessments according to the schedule of activities until the end of the double-blind treatment period, *and then the follow-up visits*, or until the last OLE follow-up visit (OLE Follow Up 2) for those who enrolled in the OLE.

The primary reason for study treatment discontinuation should be documented on the appropriate eCRF. Participants who discontinue study treatment prematurely will not be replaced.

#### **4.7.2 Participant Discontinuation**

Participants have the right to voluntarily withdraw from the study at any time for any reason. In addition, the investigator has the right to withdraw a participant from the study at any time. Reasons for withdrawal from the study may include, but are not limited to, the following:

- Participant withdrawal of consent at any time
- Study termination or site closure
- Any medical condition that the investigator *and* Sponsor determines may jeopardize the participant's safety if he or she continues in the study
- Investigator or Sponsor determines it is in the best interest of the participant

- Participant non-compliance with the study and/or study procedures, defined as missing more than three consecutive dose administrations (with Q4W dosing regimen) or more than six consecutive dose administrations (with Q2W dosing regimen) because of non-safety-related reasons or more than half of the dosing visits in a calendar year

All participants who discontinue from the study early will be asked to return 2 weeks after last dose in order to complete the early termination visit.

Participant should be informed of circumstances under which their participation may be terminated by the investigator without the participant's consent. Any administrative or other reasons for withdrawal must be explained to the participant.

Every effort should be made to obtain information on participants who withdraw from the study. The primary reason for withdrawal from the study should be documented on the appropriate eCRF. However, participants will not be followed for any reason after consent has been withdrawn.

Participants who withdraw from the study will not be replaced.

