All participants who prematurely discontinue treatment will continue participating in the study and will be asked to return for collection of safety and limited efficacy data (see Section 4.7.1).

[figure not shown]
Participants will undergo brain MRI examinations for safety monitoring and longitudinal changes in brain structure. MRI scans will be read by a central MRI reader (for more details regarding imaging-related criteria, see Section 4.1.2.2). Participants will also undergo standard tests to monitor safety (blood tests, ECG), as well as the Columbia–Suicide Severity Rating Scale (C-SSRS) to monitor for suicidality, tests for cognition, function, and QoL status. Blood samples for the assessment of PK samples, PD biomarkers, and ADA will be obtained from all participants.

The incidence and nature of adverse events, serious adverse events, ARIA-E, ARIA-H, ISRs, adverse events of special interest, ECGs, and laboratory abnormalities will be assessed on a regular basis by an unblinded iDMC.

An overview of the study design is provided in Figure 7. The schedule of activities is provided in Appendix 1.

Once the double-blind treatment period is completed, participants who consent and are eligible may opt to participate in an OLE. If the stand-alone open-label study (Study WN42171) is not open for enrollment at the time that a participant completes the double-blind treatment period of this study, then the participant will follow the OLE procedures described in this study (Section 4.3.2.2 and Appendix 1). These participants will then transition to Study WN42171 after they have completed the entire schedule of activities in the OLE of this study and the protocol for Study WN42171 is available and approved as per local requirements. If Study WN42171 is open for enrollment at the time that a participant completes the double-blind treatment period of this study, then the participant will enroll directly in Study WN42171 and not in the OLE portion of this protocol. *The OLE of Study WN39658 is not applicable in countries that cannot run Study WN42171.*

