**Figure 7 Overall Study Design**

W=week

The study consists of three distinct periods:

- Screening (including an optional pre-screening): The screening period may last up to 12 weeks for each eligible participant.
- Double-blind treatment period: After screening, participants who meet all eligibility criteria will be randomly assigned to one of two arms (gantenerumab or placebo) in a 1:1 ratio. Following baseline assessments, each participant will receive a minimum of nine SC Q4W administrations of study drug (uptitration period), followed by up to 40 administrations of study drug in the double-blind treatment period in scenario 1 or up to 46 administrations in scenario 2, if applicable. The last dose of study drug will be administered at Week 114 in scenario 1 and at Week 126 in scenario 2, if applicable. At the end of the double-blind treatment period, 2 weeks after the last dose, all participants will undergo the final safety and efficacy study visit. Participants who have already completed the double-blind treatment period prior to implementation of *the study extension by 12 weeks* will have received 34 SC Q2W administrations of study drug during the double-blind treatment period. The last dose will be administered at Week 102, and their final efficacy and safety visit will be at Week 104.
- Post-double-blind treatment period: After the final efficacy and safety study visit, all participants will be asked to come back for the long-term follow-up visits or to continue in the OLE.

Long-term follow-up: Long-term follow-up will consist of a 50-week follow-up period with evaluations at Weeks 14 and 50 after completion of study drug administration. Participants who withdraw early during the double-blind treatment period or during the OLE period are also asked to complete the long-term follow-up visits.

OLE: All eligible participants will have the opportunity to enter an OLE study.

- Eligible participants who enrolled early in the WN39658 study may start the OLE as detailed in [Appendix 1](#), [Table 5](#), and [Table 6](#), and will then transition to the open-label study WN42171 (details will be provided in protocol WN42171). Participants who terminated the WN39658 OLE early will be asked to come back for long-term follow-up visits.
- If the WN42171 protocol is available and approved by local authorities, the eligible participants will directly be enrolled in the open-label study WN42171.

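### Protocol 4.7.2 lets a missed-dose count alone end study participation, so a Week 116 CDR-SB that could have been collected may be lost

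*Protocol*

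**What the plan says.** **Leaving the study.** Protocol 4.7.2 gives the investigator the right to withdraw a participant at any time and adds: "Reasons for withdrawal from the study may include, but are not limited to, the following". One listed reason is non-compliance, defined as "missing more than three consecutive dose administrations (with Q4W dosing regimen) or more than six consecutive dose administrations (with Q2W dosing regimen") where the reason is not safety, or as missing more than half of the dosing visits in a calendar year. The definition counts doses only, and no COVID-19 exception is stated. Afterwards, "All participants who discontinue from the study early will be asked to return 2 weeks after last dose" for the early termination visit. Protocol 3.1.1 adds, in the text under Figure 7: "Participants who withdraw early during the double-blind treatment period or during the OLE period are also asked to complete the long-term follow-up visits". Section 4.7.2 also asks sites to try to obtain information on those who withdraw, and rules out follow-up only once consent is withdrawn.

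**Leaving treatment.** Protocol 3.1.1 says: "All participants who prematurely discontinue treatment will continue participating in the study". Protocol 4.7.1 says that "participants who withdraw from treatment will be asked to return for collection of safety (except MRI) and limited efficacy data", and 4.6.6 places this collection "at visits that have efficacy assessments per the schedule of activities until the end of the double-blind treatment period". Section 4.6.6 gives the early termination visit to both groups ("All participants who withdraw from treatment or discontinue from the study early"), but the scheduled efficacy visits only to those who withdraw from treatment.

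**SAP.** Section 1.2 stresses collection of the primary endpoint through Week 116, but only for participants still in the study. Section 5.3.3 uses values observed after study-drug-or-condition-related (SDCR) events and removes values observed after other (NSDCR) events. Missing values after SDCR events are imputed by copy increments from reference (CIR), and after NSDCR events under missing at random (MAR). The treatment-policy supplementary estimand in 5.3.5.2 uses all observed values.

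**The concern.** Someone who stops treatment for good keeps a scheduled Week 116 CDR. Someone who misses seven consecutive Q2W doses, but would still attend efficacy visits, may be taken out of the study and lose it. The first group is protected by three protocol sections and SAP 1.2; the second is not.

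The primary estimator would have used the lost value in two situations:

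- the withdrawal is classed SDCR, so observed data would have been kept;
- the participant would have resumed dosing without an intercurrent event, for instance with COVID-19-related gaps below the SAP threshold of 4 dose-months.

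In both, an observable primary endpoint is replaced by an imputation whose assumptions cannot be checked. If the event is NSDCR, the primary estimator discards later data anyway and the loss falls only on the treatment-policy supplementary estimand. SAP Table 3 has no row for non-compliance, so the class depends on a catch-all row or on the adjudication committee.

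**Working it through.** **Inputs.** Trigger counts: Protocol 4.7.2. Scheduled dosing, Q4W at Weeks 0-32 and Q2W at Weeks 36-114, and which visits include a CDR: Protocol Appendix 1, Tables 1-3. Late assessments, up to 4 weeks: Protocol 4.5.5. Week 116 window, Days 771-897: SAP Table 4. Dose-month weights and threshold: SAP 5.3.2. Sample size assumptions: Protocol 6.1.

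**1. The plan's own figure.** Difference = 0.30 x 2.5 = 0.75. n per arm = 2 x [2.97 x (1.960 + 1.282) / 0.75]^2 = 329.5, so 330. With the 35% allowance, 330 / 0.65 = 507.7, so 508 per arm and 1016 in total. This matches.

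**2. When the consecutive count is first met.** Q2W: 7 x 2 = 14 weeks after the last dose. Q4W: 4 x 4 = 16 weeks. The early termination visit, due at 2 weeks, is then already 12 or 14 weeks past.

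**3. Window in weeks.** (771 - 1) / 7 = 110 and (897 - 1) / 7 = 128, so Weeks 110-128.

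**4. Possible Q2W last-dose weeks, L.** Seven later doses must be missed by Week 114, so L + 14 <= 114. L = 36, 38, ..., 100, which is (100 - 36) / 2 + 1 = 33 weeks.

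**5. Which of the 33 have a scheduled CDR in the window.**

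| Visit | On time | Up to 4 weeks late |
|---|---|---|
| Early termination at L + 2 | none | none |
| Early termination held when the count is met, L + 14 | L = 96-100 (3) | L = 92-100 (5) |
| Follow-up at 14 weeks | no CDR | no CDR |
| Follow-up at 50 weeks, L + 50 | L = 60-78 (10) | L = 56-78 (12) |
| Covered | 13 | 17 |
| Not covered | 20 of 33 (61%) | 16 of 33 (48%) |

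**6. Q4W titration.** L = 0-32 puts the 50-week visit at Weeks 50-82 (at most 86 if 4 weeks late). An early termination visit held at L + 16 falls at Weeks 16-48 (at most 52). None reaches Week 110.

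**7. Against the COVID-19 event threshold.** Seven Q2W doses x 0.5 = 3.5 dose-months, below 4. Four Q4W doses x 1 = 4.0, which meets it. At the Q2W trigger, then, COVID-19-related missed doses can permit study withdrawal while not themselves being an intercurrent event in the SAP.

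**8. Power.** The documents give no withdrawal rate for this reason, so the losses below are assumptions. Starting from 330 effective per arm (90.0%), an extra loss of 1% of the 508 randomized per arm (5) gives 89.6%; 2% (10) gives 89.2%; 5% (25) gives 87.7%. If the 35% allowance already covers these losses, power is unchanged.

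**The case against.** The strongest reply is that nothing here is compulsory. The clause is discretionary, its list is illustrative, and 4.7.1 and 4.7.2 deal with different groups. A reader might infer a mandatory rule or a flat contradiction; the text supports neither. The sentence asking sites to seek information on withdrawn participants leaves room to follow anyone who still consents, though it schedules no CDR. Rewording one reason would also leave the investigator's general right to withdraw a participant intact. That point stands, and the fix has to allow for it.

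A reader might take 48-61% as the share of such participants who lose the endpoint. It is a count of calendar weeks at the first consecutive-dose trigger. It leaves out the half-of-visits criterion and unscheduled CDRs, which Protocol Appendix 1 allows and SAP 5.3.3 accepts inside the window. The true share could be lower.

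A reader might also infer heavy loss from SAP Appendix 1, which simulates 80% study drop-out after SDCR events. That is a simulation input, neither a forecast nor tied to this clause. Type I error under it was 4.69-5.18%, with missing data generated under the CIR assumption.

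Finally, withdrawal from treatment due to the pandemic is NSDCR, the 35% allowance names dropout, and a tipping-point analysis tests imputation after SDCR events. These limit the consequence. They do not replace a value that could have been observed.

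**Conclusion.** The point holds as an avoidable route to missing primary data. Missed doses alone may end study participation, and after that no provision schedules a Week 116 CDR. The early termination, follow-up and unscheduled visits may recover some values.

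The 16-20 of 33 range rests on scheduled dosing weeks, withdrawal when the consecutive count is first met, and visits on time or up to 4 weeks late. How many participants would be withdrawn this way cannot be derived from the documents. Power falls by less than 1 point if the extra loss is 2% or less, and not at all if it lies inside the allowance. No bias has been shown. The case rests on observing rather than imputing the primary endpoint where the estimator would use it; it is a worthwhile, inexpensive improvement rather than a threat to the trial.

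**What to change.** Reconcile Protocol 4.7.2 with 3.1.1, 4.6.6 and 4.7.1 in two respects:

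- missed doses alone do not end scheduled collection of the primary and secondary endpoints;
- anyone withdrawn for non-compliance who has not withdrawn consent is asked to attend the remaining scheduled efficacy visits through Week 116.

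The second part is needed because the investigator's general right to withdraw a participant remains. Dosing and treatment decisions and the right to withdraw consent are unchanged, and no view is taken on the missed-dose counts themselves.

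The cost is a protocol amendment, with ethics and regulatory approval as Protocol 9.6 requires, across about 175 centers in about 15 countries, plus continued visits for what are probably few non-compliant participants. It could be carried in an amendment made for other reasons.

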#### **4.7.3 Study Discontinuation**

The Sponsor has the right to terminate this study at any time. Reasons for terminating the study may include, but are not limited to, the following:

- The incidence or severity of adverse events in this or other studies indicates a potential health hazard to participants
- Participant enrollment is unsatisfactory
- Futility analyses suggesting that treatment with gantenerumab is likely not effective.
- Sponsor determines it is the best interest of the participants.

The Sponsor will notify the investigator if the Sponsor decides to discontinue the study.

#### **4.7.4 Site Discontinuation**

The Sponsor has the right to close a site at any time. Reasons for closing a site may include, but are not limited to, the following:

- Excessively slow recruitment
- Poor protocol adherence
- Inaccurate or incomplete data recording
- Non-compliance with the International Council for Harmonisation (ICH) guideline for Good Clinical Practice
- No study activity (i.e., all participants have completed the study and all obligations have been fulfilled)

## **5. ASSESSMENT OF SAFETY**

### **5.1 SAFETY PLAN**

Gantenerumab is not yet approved, and clinical development is ongoing. The safety plan for participants in this study is based on clinical experience with gantenerumab in completed and ongoing studies. The identified risks for gantenerumab are outlined below. Please refer to the Gantenerumab Investigator's Brochure for a complete summary of safety information.

Several measures will be taken to ensure the safety of participants enrolled in this study. Eligibility criteria have been designed to exclude participants at higher risk for imaging-related abnormalities. Participants will undergo safety monitoring during the study, including assessment of the nature, frequency, and severity of adverse events. In addition, guidelines for managing adverse events, including criteria for dosage modification and treatment interruption or discontinuation, are provided below.

#### **5.1.1 Risks Associated with Gantenerumab**

##### **5.1.1.1 Amyloid-Related Imaging Abnormalities**

To date, clinical experience with gantenerumab reveals that ARIA events are dose-dependent and *APOE*  $\epsilon$ 4 dependent. These events are manageable with MRI monitoring and dose intervention algorithms. In addition, in case of clinical symptoms, the use of IV glucocorticosteroids may be considered.

Rules for management of participants who develop ARIA-E or ARIA-H are provided in [Appendix 6](#).

##### **5.1.1.2 Injection-Site Reactions**

Gantenerumab may cause a reaction when given as an SC injection. In studies with gantenerumab, the most common events occurring more frequently with gantenerumab than with placebo were local ISRs, such as injection-site erythema. The majority of events were of mild intensity and resolved without treatment (see Section [1.2.3](#) for details).

Detailed information on the characteristic signs and symptoms of ISRs (e.g., erythema, pruritus) will be recorded on the dedicated eCRF page (see Section [5.3.5.2](#) for details on recording of ISRs).

##### **5.1.1.3 Immunogenicity**

As with administration of any exogenous protein, there is the potential for the development of ADAs, which can be neutralizing and/or sensitizing and which can potentially lead to febrile or allergic reactions, including anaphylaxis. The immunogenic risk of gantenerumab is considered low since it is a fully human antibody.

There are no clinical findings indicative of an immunogenic response to gantenerumab. Participants should be told how to recognize the signs and symptoms of hypersensitivity reactions and be monitored.

### **5.1.2 Management of Participants Who Experience Selected Adverse Events**

Participants will undergo brain MRI examinations prior to every dose increase (pre-uptitration MRI scans) and according to the schedule of activities once the target dose is achieved. The pre-uptitration MRI scans will determine eligibility for the next uptitration dose. In the double-blind treatment period, a minimum of 3 doses of each dosing step have to be administered before the participant is eligible for the next uptitration dose. In the OLE, a minimum of 3 doses of each dosing step must be administered prior to be eligible for uptitration. In the OLE, a dose is defined as two consecutive dosing visits (one with an even dose number and one with an odd dose number, see [Table 4](#), Section [4.3.2.2](#)).

Participants will be eligible for uptitration if there are no new ARIA-E, if the ARIA-E is resolved (BGTS=0), and if the criteria for discontinuation because of ARIA-H have not been met.

In addition, the following dose adjustment and discontinuation rules for MRI findings will apply:

- In case of asymptomatic ARIA-E  $\geq 1$  and  $< 4$  BGTS: Continue study drug at the same dose level (i.e., do not uptitrate) and repeat MRI 4 weeks later.
  - As long as BGTS is  $< 4$  and  $\geq 1$ , continue study drug at the same dose level and continue MRI monitoring at 4-week intervals until the event resolves. When ARIA-E resolves, resume uptitration and MRI monitoring according to the schedule of activities.
  - If BGTS  $\geq 4$  or symptoms develop, refer to the rule below.
- In case of occurrence of symptoms in the presence of ARIA-E (any size) or asymptomatic ARIA-E with  $\geq 4$  BGTS: Temporarily interrupt study drug (but continue all assessments per schedule of activities) and implement MRI monitoring performed at 4-week intervals until symptoms and ARIA resolve.
  - When symptoms and ARIA-E resolve, reintroduce study drug at the next scheduled dosing visit, at the same dose given at the time the event was detected and perform an MRI scan after the first dose for participants on Q4W regimen and after the second dose for participants on the Q2W regimen.
  - If no new ARIA-E is detected, resume uptitration and obtain an MRI scan per the titration schedule. For participants on the Q2W regimen, perform another MRI scan 3 months after study drug reintroduction.
- In exceptional cases of 1) an ARIA-E that is asymptomatic with BGTS  $< 4$  and that is considered stable over consecutive MRI images by the Sponsor and investigator; or 2) symptomatic ARIA-E for which the imaging evidence of ARIA-E has resolved but

the CNS symptoms continue, the study drug can either be reintroduced or uptitrated, as applicable, and 4-weekly MRI monitoring may no longer be necessary, as determined by the Sponsor and investigator.

- Symptomatic ARIA-E is defined as onset or worsening of CNS symptom(s) that is/are temporally associated with ARIA-E MRI findings.
- Any recurrence of ARIA-E: Treat using the same procedures as for the first event (based on symptoms and BGTS).
- Participants who develop > 15 ARIA-H cumulatively will be discontinued from study drug (the cumulative number should not include any disseminated leptomeningeal hemosiderosis, i.e., up to 3 focal leptomeningeal hemosiderosis *either on the same scan or cumulatively*; a focal leptomeningeal hemosiderosis is counted as an ARIA-H).
- In cases where both ARIA-E and ARIA-H occur, the most conservative approach should be followed.
- A PK sample and a plasma biomarker sample will be obtained as soon as is practical (e.g., at an unscheduled visit) once the site becomes aware of the occurrence or worsening of ARIA-E or ARIA-H that meet the discontinuation criteria.
- The investigators may choose to perform additional MRI monitoring for ARIA at any time.
- MRI monitoring of ARIA findings should be conducted at approximately 4-week intervals.
- Any other new significant findings will be reviewed by the medical monitor and appropriate dose action will be taken.

The iDMC reviews the incidence of ARIA in an unblinded manner and may recommend adjustment of dosing regimen and/or ARIA management for the overall study population or for a specific *APOE* ε4 genotype.

